6.1 Study treatment

Treatment Period 1:

The study treatment will consist of INC424 (ruxolitinib) or matching placebo administered in a blinded manner following randomization of the patient on study Day 1.

Treatment Period 2:

INC424 (ruxolitinib) administered as per [Table 6-1](#).

Table 6-1 Starting Doses of INC424 based on platelet counts (Treatment Period 2)

INC424	Platelet count (x 10 ⁹ /L)
5 mg BID	50 – <100
15 mg BID	100 – 200
20 mg BID	>200

6.1.1 Dosing regimen

Table 6-2 Dose and treatment schedule

Treatment Period 1 (INC424/Placebo - Blinded)

Study treatments	Pharmaceutical form and route of administration	Dose	Frequency and/or Regimen
INC424/ Placebo	Tablet for oral use	10 mg BID (2 tablets of INC424 5mg/placebo BID)	Daily

Study treatment will be administered orally twice per day at a dose of 10 mg BID, given as 2 tablets of INC424 5mg / placebo ([Table 6-2](#)). Study treatment should be taken orally twice daily, approximately 12 hours apart (morning and night) without regards to food. Study treatment will be self-administered by the patient in an outpatient setting, and each investigator should instruct the patient to take the study drug as per protocol. All dosages taken by the patient must be recorded on the Dosage Administration Record case report form (CRF).

Patients should be instructed not to take study treatment at Week 12, Week 24 and Week 48 visit (and every 12 weeks thereafter) on the day of the scheduled pre-dose blood collection ([Section 7](#)). Dosing will be administered post blood collection at these visits.

Treatment Period 2 (INC424)

Once the patient progresses in Treatment Period 1 by splenomegaly or symptoms, the patient will start treatment with INC424 (ruxolitinib) 5/15/20 mg BID based on platelet count as per approved label ([Table 6-1](#) and [Table 6-3](#)).

Table 6-3 Dose and treatment schedule

Treatment Period 2 (INC424)

Study treatments	Pharmaceutical form and route of administration	Dose	Frequency and/or Regimen
INC424	Tablet for oral use	5/15/20 mg BID	Daily

6.1.2 Ancillary treatments

Not applicable.

6.1.3 Rescue medication

Not applicable.

6.1.4 Guidelines for continuation of treatment

Refer to [Section 6.3](#) on dose modifications and follow up for toxicities for guidelines for continuation of treatment.

6.1.5 Treatment duration

Patient may continue treatment with the study drug until patient experiences unacceptable toxicity, disease progression and/or treatment is discontinued at the discretion of the investigator or patient.

6.2 Dose escalation guidelines

Not applicable.

6.3 Dose modifications

6.3.1 Dose modification and dose delay

6.3.1.1 Dose modification for hematologic toxicity

Treatment Period 1

Dose reductions or interruptions for hematological changes are permitted in order to allow the patient to continue on the study treatment. The maximum allowed doses for different ranges of cytopenia is described in [Table 6-4](#). The objective of the dose adjustment rules is to optimize treatment response for each individual patient while avoiding significant cytopenia. Dosing may be restarted or increased following recovery of the hematologic parameter(s) to acceptable levels. Any patient requiring dose interruption continuously for more than 4 weeks

due to decreases in ANC or platelet (PLT) counts must be permanently discontinued from treatment. Hb levels decreasing below 8g/dL with an absolute drop of 3g/dL from baseline, will constitute a marker of progressive MF disease, if Hb levels fail to recover \geq 8g/dL following treatment interruption for two consecutive weeks. Such patients must permanently discontinue study treatment.

Table 6-4 Dose reductions and interruptions due to hematological changes – Treatment Period 1

Current Hb (g/dL)	Maximum allowable dose
< 8	Interrupt dosing (HOLD)
8 to < 10	Reduce total daily dose to 5 mg BID
Current PLT ($\times 10^9/L$)	
< 50	Interrupt dosing (HOLD)
50 to < 75	Reduce total daily dose to 5 mg BID
Current ANC ($\times 10^9/L$)	
< 0.5	Interrupt dosing (HOLD)
0.5 to < 0.75	Reduce total daily dose to 5 mg BID

All dose changes must be recorded on the Dosage Administration Record CRF.

Patients whose dose has been interrupted for more than 4 weeks for any reason are recommended to be permanently discontinued from study treatment.

Treatment Period 2

Dose reductions and interruptions for ruxolitinib treatment during ‘Treatment Period 2’ can be performed in accordance with the local label requirements. In countries where ruxolitinib is not currently approved, treatment should be discontinued for platelet counts less than $50 \times 10^9/L$ or absolute neutrophil counts less than $0.5 \times 10^9/L$. After recovery of blood counts above these levels, dosing may be re-started at 5 mg twice daily and gradually increased based on careful monitoring of complete blood cell count, including a white blood cell count differential.

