Ruxolitinib has previously demonstrated marked reductions in disease related spleen sizes and symptom improvements in patients with advanced MF. Although the inclusive population in the current study have relatively early disease with minimal or no splenomegaly or disease related symptoms, it is hypothesized that ruxolitinib would delay progression of underlying disease and therefore benefit patients by delaying the time to acquiring these bothersome disease related events. It is anticipated that ruxolitinib will also be associated with reductions in inflammatory cytokine levels.

In summary, while early institution of treatment in the studied population and the expectant duration of treatment may increase the likelihood of some adverse events, the lower dose of ruxolitinib used in the study, the relatively better general physical status of the patients at study entry and the anticipated benefit of maintaining this status over prolonged periods, is expected to confer participating patients with an overall therapeutic advantage with acceptable tolerability.

Please refer to the study-specific informed consent form for further information.

3 Objectives and endpoints

Objectives and related endpoints are described in [Table 3-1](#) below.

[figure not shown]
[figure not shown]
[figure not shown]
[figure not shown]

Table 3-1 Objectives and related endpoints

Objective	Endpoint	Analysis
Primary		
To evaluate the effect of ruxolitinib in delaying progression of MF from early disease to advanced disease	Progression free survival (PFS-1) from date of randomization until the occurrence of any of the criteria for disease progression (See Section 10.4.1 for details on criteria and required confirmation): 
 • Progressive splenomegaly • Circulating peripheral blast counts > 10% • Leukemic transformation • Hb < 10g/dl with absolute decrease of at least 3 g/dl from baseline • White blood cell (WBC) counts > 25 x 10³/ μL • MF-7 score ≥ 30 • Death from any cause 	Refer to Section 10.4 Refer to Section 10.4.1
Secondary		
To evaluate time to disease progression of MF with or without ruxolitinib	Time to primary progression	Refer to Section 10.5
To evaluate the changes in spleen volume with or without ruxolitinib	Time to first progressive splenomegaly as determined by spleen volume (by MRI/CT) Change in spleen volume (by MRI/CT) from baseline	

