5.2 Inclusion criteria

Patients eligible for inclusion in this study have to meet **all** of the following criteria at screening:

Written informed consent must be obtained prior to any screening procedures.

1. Male or Female aged 18 or over.
2. Confirmed diagnosis of MF with bone marrow fibrosis of at least Grade 1 ([Appendix 2](#)); irrespective of JAK2 mutational status.

3. Patients with at least one mutation in one of the five HMR genes (ASXL1, EZH2, SRSF2 and IDH1/2).
4. Patients with non-palpable spleen or spleen palpable ≤ 5 cm from the left costal margin to the point of greatest splenic protrusion.
5. Patients with MF-7 score of ≤ 15 , with each individual symptom score of ≤ 3 .
6. Patients with a peripheral blood blast count percentage of $< 1\%$.
7. Patients with Hemoglobin $> 10\text{g/dL}$.
8. Patients with platelet counts $\geq 75,000/\mu\text{L}$.
9. Patients with Absolute neutrophil count (ANC) $\geq 1000/\mu\text{L}$.
10. Patients with WBC $\leq 15 \times 10^3/\mu\text{L}$.
11. Patients with an Eastern Cooperative Oncology Group (ECOG) performance status of 0, 1, or 2.

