7.1.4 Treatment Period

Treatment Period 1

Blinded study treatment will be initiated on Day 1 after randomization and treatment assignment by IRT system. Day 1 is defined as the first day of study treatment. After day 1, visits will occur at the following frequency as specified in Table 7-1.

- Every 4 weeks until week 24 (+/- 3 days)
- Every 8 weeks until week 48 (+/- 7 days)
Note: Week 36 visit is required only for MRI/CT of the spleen.
- Every 12 weeks until the end of treatment (+/- 7 days)

Blinded treatment will be administered until disease progression or patient discontinuation.

Treatment Period 2

[figure not shown]
Patients progressing due to splenomegaly or symptom (MF-7 score) in Treatment Period 1 will enter the ruxolitinib Treatment Period 2. All patients are required to have an End of Treatment Period 1 assessment prior to entering Treatment Period 2. All End of Treatment Period 1 assessments should be performed within 2 weeks prior to the first dose of ruxolitinib in Treatment Period 2. The End of treatment bone marrow biopsy and MRI/CT assessments should follow the schedule as per Section 7.2.1.1. The schedule of assessments for patients entering Treatment Period 2 will continue from when the patient discontinued in Treatment Period 1 (Table 7-1 [B]).

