10.4.1 Variable

The primary endpoint is **progression free survival (PFS-1) in Treatment Period 1**. It is defined as the time from date of randomization until earliest time for one of the following events:

- Progressive splenomegaly as assessed by doubling of spleen volume (by MRI/CT); in addition to an absolute spleen volume of greater than 450 cm³.
- Circulating peripheral blast counts > 10% (requires confirmation after 8 weeks)
- Leukemic transformation defined by an increase in peripheral blood blast percentage to $\geq 20\%$ that is sustained for at least 8 weeks or a bone marrow blast count of $\geq 20\%$
- Hb < 10g/dl with an absolute decrease of at least 3 g/dl from baseline levels (requires confirmation following 2 week of dose interruption/reductions to ensure this is not drug induced cytopenia. In case of Hb stabilizing following dose modification within the 2 weeks, study drug can be re-escalated based on investigators discretion. See section 6.3 for guidance on dosing modifications)
- WBC counts > 25 x 10³/ μ L

- Confirmed MF-7 score of ≥ 30 in addition to an individual symptom score of ≥ 7 in at least one non-splenomegaly related symptom, i.e., tiredness, night sweats, itching (pruritus), bone pain (diffuse not joint pain or arthritis). (Confirmed on two consecutive weeks)
- Death from any cause

As the proposed study intends to investigate the benefit of ruxolitinib in delaying the emergence of MF associated symptoms, MF-7 is expected to objectively evaluate disease progression based on the worsening of symptoms through symptom scores. A clinically relevant threshold of ≥ 30 was set to capture the time point when the patient begins experiencing more symptomatic disease (disease progression) reflected by a minimum of doubling in the baseline MF-7 scores. Additionally, progression by symptom will also require an individual score of ≥ 7 in at least one non-splenomegaly related symptom, i.e., tiredness, night sweats, itching (pruritus), bone pain (diffuse not joint pain or arthritis).

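### Protocol 6.3.1.1 and 10.4.1 set different hemoglobin thresholds and recheck tests for progressive MF in Treatment Period 1, and the 6.3.1.1 stop is not tied to or separated from PFS-1 (minor)

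*Protocol*

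**What the plan says.** **The 6.3.1.1 rule (Treatment Period 1).** "Hb levels decreasing below 8g/dL with an absolute drop of 3g/dL from baseline, will constitute a marker of progressive MF disease". The attached condition is that Hb does not return to 8 g/dL or more "following treatment interruption for two consecutive weeks. Such patients must permanently discontinue study treatment". Table 6-4 in the same section holds dosing below 8 g/dL and reduces the dose from 8 to below 10 g/dL.

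**The PFS-1 rule.** Table 3-1 lists "Hb < 10g/dl with absolute decrease of at least 3 g/dl from baseline" and refers to 10.4.1 for the criteria and their confirmation. Section 10.4.1 repeats that threshold and drop and adds that the finding "requires confirmation following 2 week of dose interruption/reductions to ensure this is not drug induced cytopenia". Its only words on recovery are "In case of Hb stabilizing following dose modification within the 2 weeks, study drug can be re-escalated based on investigators discretion". Its pointer to the dosing section reads "See section 6.3 for guidance on dosing modifications".

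**Which section governs.** Sections 7.1.5, 7.2.1.1 (including its laboratory item) and 8.1.1 all refer to 10.4.1 for progression. Section 7.1.5 also lists, as separate grounds for mandatory discontinuation, progression under 10.4.1 and dose modifications under 6.3.

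**What follows a stop.** "Patients progressing due to splenomegaly or symptom (MF-7 score) in Treatment Period 1 will enter the ruxolitinib Treatment Period 2", so progression by Hb alone does not open that route. Under 7.1.7.1 a stop for progression leads to survival follow-up. Under 7.1.7.2 a stop for another reason keeps hematology, spleen imaging and MF-7 assessments going.

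**SAP amendment 1.** PFS is not derived (2.5), and patient numbers and study duration were minimal (1.2). The primary reason for discontinuation is tabulated (2.3.1).

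**The concern.** Both sections speak of progressive disease, in the same treatment period, on the same laboratory value, and each leads to a mandatory stop. They use different thresholds (8 versus 10 g/dL) and different recheck tests (a numeric level versus none). Section 6.3.1.1 neither cites 10.4.1 nor says that its marker is something other than a PFS-1 event.

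Hb is a component of the primary endpoint. The protocol also describes anemia as a dose-related drug effect (1.2.1.2.3, 2.5), so the recheck is what separates drug effect from progression. The label put on the stop decides the reason recorded and which assessments continue afterwards.

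**Working it through.** The plan states no figure to reproduce. The check applies both rules literally to hypothetical Hb values.

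**Inputs.** Let b be baseline Hb, which must exceed 10 g/dL at entry (5.2, criterion 7). Let h1 be the Hb at first occurrence and h2 the Hb at the two-week recheck. All values are in g/dL, in steps of 0.1. The drop of 3 g/dL in 6.3.1.1 is read as at least 3.

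**Step 1: first occurrence.**
- 6.3.1.1: h1 < 8 and b − h1 ≥ 3
- 10.4.1: h1 < 10 and b − h1 ≥ 3

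Both need h1 ≤ b − 3. If b < 11, then b − 3 < 8, so the drop is the binding condition and the rules coincide. From b = 11.0 upward, 10.4.1 alone is met from 8.0 up to b − 3, and always below 10:

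| Baseline | Hb values meeting 10.4.1 only |
|---|---|
| above 10 and below 11 | none |
| 11.0 | 8.0 |
| 11.5 | 8.0 to 8.5 |
| 12.0 | 8.0 to 9.0 |
| 12.5 | 8.0 to 9.5 |
| 13.0 or more | 8.0 to below 10 |

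On a grid with b from 10.1 to 16.0 and h1 from 5.0 to 10.0 there are 60 × 51 = 3,060 pairs. Of these, 830 meet 10.4.1 only and none meets 6.3.1.1 only.

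**Step 2: recheck.** Under 6.3.1.1 the marker stands if the step 1 condition was met and h2 < 8. Section 10.4.1 does not say what confirmation requires, so two readings were tried:
- Reading A: the full criterion is met again, that is h2 < 10 and b − h2 ≥ 3.
- Reading B: only h2 < 10 is needed.

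Worked cases:
- b = 12.0, h1 = 7.8, h2 = 8.5. The first drop is 12.0 − 7.8 = 4.2, so both rules are triggered. At recheck 8.5 ≥ 8, so the patient has recovered under 6.3.1.1. But 8.5 < 10 and 12.0 − 8.5 = 3.5 ≥ 3, so 10.4.1 is met under A and B.
- b = 10.5, h1 = 7.4, h2 = 7.8. The first drop is 3.1, so both rules are triggered. At recheck 7.8 < 8, so 6.3.1.1 requires a stop. The drop is now 10.5 − 7.8 = 2.7 < 3, so 10.4.1 is not confirmed under A. Under B it is confirmed and the rules agree.
- b = 10.5, h1 = 7.4, h2 = 8.5. The patient has recovered under 6.3.1.1. Section 10.4.1 is met under B and not under A.

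Adding h2 from 5.0 to 12.0 gives 3,060 × 71 = 217,260 triples:

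| Reading of 10.4.1 | 6.3.1.1 only | 10.4.1 only |
|---|---|---|
| A | 876 (baselines 10.1 to 10.8) | 65,070 (baselines 11.0 to 16.0) |
| B | 0 | 76,780 (baselines 10.1 to 16.0) |

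The upper limit of 10.8 follows because a case meeting 6.3.1.1 only needs b − 3 < h2 ≤ 7.9, hence b < 10.9. These counts show where and in which direction the rules part. They say nothing about how many patients would be affected.

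**Step 3: confirming action.** Section 6.3.1.1 names interruption only, while 10.4.1 names interruption or reduction. Table 6-4 holds below 8 g/dL and reduces from 8 to below 10 g/dL. The 6.3.1.1 sentence covers only the lower band and 10.4.1 covers both, so the two wordings fit together.

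**The case against.** A reader might infer that the primary endpoint itself is undefined. The documents do not support that. Table 3-1, 7.1.5, 7.2.1.1 and 8.1.1 all send progression to 10.4.1, and none sends it to 6.3. What counts as a PFS-1 event by threshold and drop can be identified.

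A reader might also count the interruption versus reduction wording as a further conflict. Step 3 shows that it is not one.

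A third tempting reading is that the rules disagree in both directions. The direction in which 6.3.1.1 alone is met exists only under Reading A and only for baselines of 10.1 to 10.8. Under Reading B there are no such cases.

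The strongest remaining defense is that both rules can be obeyed together. Section 6.3.1.1 gives one sufficient marker and does not say that Hb from 8 to below 10 g/dL is never progression. Table 6-4 sets a maximum dose, not an instruction to continue after confirmed progression. Section 7.1.5 lists both stops, so a site following the whole protocol stops when either is met. That defense largely stands for the decision to stop, and it reduces the issue mainly to how the stop is labeled. It does not explain why a patient who has recovered by one section's test should still be a confirmed progression by the other's. Nor does it say whether a 6.3.1.1 stop is to be recorded as progression.

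**Conclusion.** The text is wrong as written, and the matter is minor. The conflict lies in the Hb threshold (8 versus 10 g/dL) and in the recheck test (8 g/dL or more versus no numeric level). At first occurrence it is confined to baselines of 11.0 g/dL or more, always with 10.4.1 alone being met. At recheck a patient can be recovered under 6.3.1.1 and still meet 10.4.1.

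The recheck results assume that confirmation means Reading A or B. Because 10.4.1 speaks only of stabilizing, an investigator could also judge that 8.5 g/dL is stable, and the text gives no value to settle it.

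The remaining effect is on the tabulated reason for discontinuation and on whether later hematology, spleen and MF-7 data were collected. It would be wrong to infer that results were distorted or patients mishandled. PFS is not derived, numbers and duration were minimal, and the documents show no patient who met one rule and not the other. The SAP also already lists disposition (2.3.1), dosing records (2.4) and laboratory values (2.8.3).

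**What to change.** Reconcile 6.3.1.1 with 10.4.1 on the Hb threshold and on the recovery or confirmation test. State whether a 6.3.1.1 stop is recorded as PFS-1 progression or as a dose-modification discontinuation. The clinical team decides the content; this review takes no view on which rule is right. Table 3-1 already agrees with 10.4.1 on threshold and drop, and 7.1.5 only cross-refers, so neither needs a change unless 10.4.1 changes.

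In the abbreviated CSR, add a note stating, for any Hb-based progression or discontinuation, which rule was applied. If there were none, say so.

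The cost is a wording change in two sections and one note from data already collected. Rewording cannot alter how the terminated trial was run, so the CSR note is the part that can still help.

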6.3.1.2 Dose modification for non-hematological toxicity (Treatment Period 1 and 2)

Study drug MUST be permanently discontinued upon the occurrence of a clinically significant Grade 3 or Grade 4 laboratory or non-laboratory abnormality attributed to ruxolitinib if it fails to resolve to Grade 2 or better within 8 weeks or if a lower re-start dose or administration schedule is either not available or likely to be clinically ineffective. Specific recommendations that are to be followed in the event of abnormal liver function tests are provided in [Table 6-5](#).

[figure not shown]
[figure not shown]
[figure not shown]

Table 6-5 Dose modifications for abnormal liver function tests

Isolated Elevation of Total Bilirubin	
> ULN – 1.5 x ULN	Maintain dose level
>1.5x baseline AND > 1.5 - 3.0 x ULN	Omit dose with weekly monitoring of LFTs ^a , or more frequently if clinically indicated, until resolved to ≤ 1.5 x ULN or baseline levels - If resolved in ≤ 14 days, then maintain dose level - If resolved in > 14 days, then ↓ 1 dose level ^d
> 3.0 - 10.0 x ULN	Omit dose with weekly monitoring of LFTs ^a , or more frequently if clinically indicated, until resolved to ≤ 1.5 x ULN or baseline levels - If resolved in ≤ 14 days, then ↓ 1 dose level ^d - If resolved > 14 days, discontinue patient from study drug treatment. The patient should be monitored weekly (including LFTs ^a), or more frequently if clinically indicated, until total bilirubin have resolved to baseline levels or have remained stable over 4 weeks.
> 10.0 x ULN	Discontinue patient from study drug treatment. The patient should be monitored weekly (including LFTs ^a), or more frequently if clinically indicated, until total bilirubin have resolved to baseline levels or have remained stable over 4 weeks.

Isolated AST or ALT elevation	
> ULN - 3.0 x ULN	Maintain dose level
> 3.0 - 5.0 x ULN	Maintain dose level. Repeat LFTs ^a as soon as possible, preferably within 48-72 hours from awareness of the abnormal results; if abnormal lab values are confirmed upon the repeat test, then monitor LFTs ^a weekly, or more frequently if clinically indicated, until resolved to ≤ 3.0 x ULN
> 5.0 - 10.0 x ULN	Omit dose. Repeat LFTs ^b as soon as possible, preferably within 48-72 hours from awareness of the abnormal results; monitor LFTs ^b weekly, or more frequently if clinically indicated, until resolved to ≤ 3.0 x ULN Then - If resolved in ≤ 14 days, maintain dose level - If resolved in > 14 days, ↓ 1 dose level

 For patients with baseline value ≤ 3.0 x ULN 	

 For patients with baseline value > 3.0 -5.0 x ULN 	Maintain dose level. Repeat LFTs ^b as soon as possible, preferably within 48-72 hours from awareness of the abnormal results; if abnormal lab values are confirmed upon the repeat test, then monitor LFTs ^b , weekly, or more frequently if clinically indicated, until resolved to ≤ 5.0 x ULN
> 10.0 - 20.0 x ULN	Omit dose. Repeat LFTs ^b as soon as possible, preferably within 48-72 hours from awareness of the abnormal results; monitor LFTs ^b weekly, or more frequently if clinically indicated, until resolved to ≤ baseline. Then ↓ 1 dose level.
> 20.0 x ULN	Discontinue patient from study drug treatment AND Repeat LFTs ^a as soon as possible, preferably within 48-72 hours from awareness of the abnormal results; monitor LFTs ^a weekly, or more frequently if clinically indicated, until resolved to baseline levels or have remained stable over 4 weeks.

Combined^b elevations of AST or ALT and total bilirubin

For patients with normal baseline ALT or AST or total bilirubin value:

AST or ALT >3.0xULN combined with total bilirubin >2.0 x ULN without evidence of cholestasis^c

OR

[figure not shown]
[AST or ALT>2x baseline AND > 3.0 xULN] OR [AST or ALT > 8.0 xULN], whichever is lower, combined with [total bilirubin >2x baseline AND >2.0 xULN without evidence of cholestasis^c

Permanently discontinue patient from study drug treatment;

AND

Repeat LFTs^a as soon as possible, preferably within 48 hours from awareness of the abnormal results, then with weekly monitoring of LFTs^a), or more frequently if clinically indicated, until AST, ALT, or bilirubin have resolved to baseline or have remained stable over 4 weeks. Refer to [Section 6.3.2.1](#) for additional follow-up evaluations as applicable.

a. Core LFTs consist of ALT, AST, GGT, total bilirubin (fractionated [direct and indirect], if total bilirubin > 2.0 x ULN), and alkaline phosphatase (fractionated [quantification of isoforms], if alkaline phosphatase > 2.0 x ULN.)
b. “Combined” defined as: total bilirubin increase to the defined threshold concurrently with ALT/AST increase to the defined threshold
If combined elevations of AST or ALT and total bilirubin do not meet the defined thresholds, please follow the instructions for isolated elevation of total bilirubin and isolated elevation of AST/ALT, and take a conservative action based on the degree of the elevations (e.g. discontinue treatment at the situation when omit dose is needed for one parameter and discontinue treatment is required for another parameter). After all elevations resolve to the defined thresholds that allow treatment re-initiation, re-start the treatment either at the same dose or at one dose lower if meeting a criterion for dose reduction
c. “Cholestasis” defined as: ALP elevation (>2xULN and R value <2) in patients without bone metastasis, or elevation of ALP liver fraction in patients with bone metastasis
Note : The R value is calculated by dividing the ALT by the ALP, using multiples of the ULN for both values. It denotes the relative pattern of ALT and/or ALP elevation is due to cholestatic or hepatocellular liver injury
d. Total daily dose 10 mg (5 mg BID) lower than the previous dose

